6.3.2 Laboratory measurement of glucose and lipid metabolism

Leptin, adiponectin, HOMA-IR, HbA1c, fasting glucose, insulin, c peptide and lipids will be measured.

6.3.3 Laboratory measurement of estradiol and estrone

Oestradiol and estrone will be measured by a validated sensitive mass spectrometry (28). If further precision is required, an ultrasensitive estradiol method with a limit of qualification (LOQ) of 0.25pg/ml with accuracy (93-110%) and precision (median coefficients of variation 4%, all concentrations above LOQ <15%). The Austin Health researchers will be collaborating with [name] from the ANZAC Research Institute in Sydney to enable very accurate measurement of hormone levels in the blood samples

6.3.4 Mood and exercise frequency by validated questionnaires and accelerometer measurements

Mood will be assessed via the Functional Assessment of Cancer Therapy-Breast (FACT-B) and Menopause-Specific Quality of Life (MENQOL) tools and physical activity levels via the accelerometer measurements.

6.3.5 Abdominal aortic calcification by DXA

Abdominal aortic calcification will be calculated using the lateral spine images acquired via DXA. The Abdominal aortic calcification score calculated will then be interpreted.

6.3.6 Endothelial dysfunction via EndoPAT

Peripheral microvascular endothelial dysfunction will be measured via the EndoPAT device (endo-PAT2000 version 3.2.4; Itamar Medical Ltd, Caesarea, Israel). All women including those with previous axillary lymph node or sentinel lymph node surgery will be included, but their surgical arm will be used as a control. Patients should be fasted prior to testing but can have water. Medications that affect vascular tone should be withheld that morning. A baseline blood pressure done on the surgical arm will be used as a control blood pressure. This control blood pressure (BP) will determine how high the systolic blood pressure on the experimental (nonsurgical) arm will need to be increased to (200mmHg or 60mmHg above the systolic – whichever is higher). There is currently no strong evidence in the literature for increased lymphoedema risk with the measurements of blood pressure in these women. This has also been discussed at the Austin Health Oncology multidisciplinary meeting where the consensus between oncologists and surgeons is that blood pressure measurements on the side of previous axillary lymph node surgery is acceptable. Arm circumference measurements will be monitored throughout the study. Patients with a previous known diagnosis of lymphoedema will not have blood pressure measurements performed on the affected arm and the target BP will be set at 200mmHg in the experimental arm.

6.3.7 Hepatic steatosis via fibroscan

Fibroscan will be used to determine steatosis/fibrosis. Patients are required to be fasting prior to the procedure. All patients with abnormal findings will be referred on to the gastroenterology clinic.

6.3.8 Anthropometric data

This will include clinical measurements of height, weight, BMI, waist circumference, hip circumference and waist:hip ratio.

6.3.9 Routine Bloods

Baseline: FBE, UEC, CMP, LFT, AST, ctx, p1np, 25 OH Vit D, oestradiol, FSH, LH, IGF-1, SHBG, PTH, CRP, TSH, FT3, FT4, IgA, Anti-gliadin ab, TTG Ab

Review: FBE, UEC, CMP, LFT, AST, ctx, p1np, 25 OH Vit D, oestradiol, FSH, LH IGF-1, SHBG, PTH, CRP

6.4 Follow up

All patients will be followed up for a total of 24 months over a total of 4 study visits.

7. PARTICIPANT SAFETY AND WITHDRAWAL

7.1 RISK MANAGEMENT AND SAFETY

Participants will be informed that there is a risk that performing some of the tests may distress them, either physically or emotionally. Fully trained staff will perform all tests which will minimise this risk. There may be additional risks that researchers do not expect. Any adverse events will be managed at Austin Health and would be free of charge as a public patient.

1. Possible risks associated with ionising radiation

This research study involves exposure to a very small amount of radiation. Compared to background radiation exposure of 2 millisiverts (mSv) per year, the effective dose from this study is approximately 0.24 mSv. At this dose level, no harmful effects of radiation have been demonstrated, as any effect is too small to measure. The risk is believed to be minimal.

2. Possible risks associated with blood tests

Venepuncture can cause some discomfort and bruising. Infection is extremely rare following venepuncture.

3. **Discomfort associated with inflation of blood pressure cuff during measurements of peripheral arterial microvascular function**

Blood pressures will be done with the aim to reach 200mmHg or 60mmHg above the patient's systolic blood pressure. This can cause some discomfort and temporary paraesthesia. These blood pressures will only be performed on the non-surgical arm with a

normal blood pressure to be performed on the surgical arm. Patients with known lymphoedema will not have a blood pressure performed on the surgical arm.

4. Psychological distress

We do not envisage that this study will cause any participant psychological distress. If participants do experience distress, they will be encouraged to speak to the study doctors. An appropriate level of care will be triaged by the study doctors. This may include withdrawal from the study, referral to a general practitioner or Austin Health psychologist/psychiatrist for psychological support.

7.2 HANDLING OF WITHDRAWALS

Participants who wish to withdraw from the study or who need to be withdrawn for other reasons will be reviewed by a study doctor to discuss this. It will be clear to them throughout the trial at that time, that withdrawal will not negatively impact their relationship with their treating doctor, or Austin Health. No additional personal, blood samples or health information will be collected from participants who withdraw.

8. STATISTICAL METHODS

8.1 STATISTICAL METHODS TO BE UNDERTAKEN

Longitudinal changes in the primary and secondary endpoints will be analyzed using paired-sample t-tests, generalised linear mixed models and generalised estimating equations and compared between patients with and without AI therapy. Adjustments will be made for age, comorbidities and baseline measurements.

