Inclusion Criteria:	
Women must meet all inclusion criteria to participate:
 
 - Postmenopausal women with oestrogen-receptor positive non-metastatic breast cancer (TxMxM0) based on documented pathological and radiological evaluation - Ages 50-85 years (post-menopausal) 
Endocrine Therapy group:
 
 - Set to commence endocrine therapy as determined by the treating oncologist/commenced ET for no more than 8 weeks prior to recruitment 
OR
 
Control group:
 
 - Ductal carcinoma insitu (DCIS) – any grade not on ET/ Early stage, non-metastatic breast cancer not requiring ET - Treatment intended for at least 12 months - Eastern Cooperative Oncology Group (ECOG) 0 and 1 - Able to independently read and understand the participant information and consent form and provide written, signed and dated data informed consent to participate in the study - Able and willing to meet all protocol required procedures and visits
Exclusion Criteria:	
 - Cessation or switching ET during the 12 month study period

	
 - Previous hormone replacement therapy within 12 months of study recruitment - Glucocorticoid use (continuously for ≥ 2 weeks within the 6 months prior to screening) - Malignancy within the past 5 years including breast cancer requiring treatment (except non-melanoma skin cancers) - Established type 2 diabetes mellitus - Any disease which is likely to lead to serious illness or death within the study period - Self reported recreational drug use or alcohol dependence within 12 months of screening
Number of Planned Participants:	130
Statistical Methods:	
 • Longitudinal changes in the primary and secondary endpoints will be analyzed using paired-sample t-tests, generalised linear mixed models and generalised estimating equations and compared between patients with and without endocrine therapy • Adjustments will be made for age, comorbidities and baseline measurements
Subgroups:	
Tamoxifen Chemotherapy ER+ and HER2+ disease – commencing Herceptin as well as endocrine therapy Premature menopause/hysterectomy (<40yrs)

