3.2.2 Effects of Profound Oestradiol Deprivation on Body Composition

The distribution of fat, more so than BMI, is what has been clinically correlated with the development of cardiometabolic disturbances. Increased visceral adipose tissue (VAT), is not only associated with the multiple risk factors for CVD, such as insulin resistance, hypertriglyceridemia, hypertension and chronic inflammation, but is also known to independently increase risk of CV events (12) – making it a significant risk factor that potentially can be targeted and reversed.

Changes in waist circumference and body composition, including reductions in lean body mass and an increased propensity for weight gain and increased fat VAT have been associated with the menopausal state (9,10). Replacement of E2 via menopausal hormone therapy is associated with reduced total and visceral adiposity, suggesting these changes in body composition are the result of E2 deficiency rather than of age per se (11).

To date, the effect of “virtually complete” E2 deprivation on body composition remains unclear. There are only a few studies examining the effects of E2 deprivation as a result of AI treatment on body composition in postmenopausal women, with the only randomized controlled trials in the current literature comprising mainly of small studies (ranging from 56 to 82 participants) with participants having had previous exposure to tamoxifen and/or adjuvant chemotherapy (7, 8, 13). Control groups were exposed to ongoing tamoxifen which is an important confounder of changes to body composition and lipid profile. The only observational study describing the effects of AI therapy on VAT observed an increase in visceral adipose tissue in women treated with AI therapy for 6 months compared to baseline. The retrospective study had small numbers (n=64), and importantly lacked a control group. Moreover, participants had previous exposure to chemotherapy which in itself may affect body composition due to effects on food intake, activity levels and concomitant glucocorticoid therapy (14). There are currently no prospective studies that investigate the effects of profound E2 deprivation as a result of AI therapy alone. Furthermore, apart from the previously described retrospective uncontrolled, observational study, none of the current studies have assessed VAT.

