4.3 OUTCOME MEASURES

Patients receiving each form of endocrine therapy (AI, tamoxifen, control) will be compared across groups with respect to the following primary and secondary endpoints.

1. Primary Endpoints

- Changes in visceral adiposity tissue at 12 months in women using aromatase inhibitors versus controls (DCIS/early stage breast cancer not requiring ET) as measured by DXA

Changes in subcutaneous adiposity tissue, fat and lean mass at 12 months in women using aromatase inhibitors versus controls (DCIS/early stage breast cancer not requiring ET) as measured by DXA

2. Secondary endpoints:

- Changes in body composition in women using tamoxifen at 12 months (measured by DXA, hologic) versus controls (DCIS/early stage breast cancer not requiring ET)
- Changes in glucose metabolism (measured by HOMA-IR, fasting glucose, insulin, c peptide, HbA1c and adiponectin, leptin levels) at 12 months
- Changes in lipid metabolism (measured by serum lipids) at 12 months
- Changes in abdominal aortic calcification (measured by DXA) at 12 months
- Changes in peripheral microvascular endothelial function (measured by EndoPAT) at 12 months
- Changes in degree of hepatic steatosis (measured by fibroscan and liver function tests) at 12 months
- Changes in visceral and subcutaneous abdominal fat volume and distribution (anthropometric measurements) at 12 months
- Changes in behaviour, mood and lifestyle (Assessment tools to determine any significant changes in appetite and exercise) at 12 months
- Changes in sex steroids at 12 months
- Changes in bone remodelling markers (ctx, p1np) at 12 months

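### The two statistical-methods sentences define different group comparisons (AI versus no AI in Section 8.1, ET versus no ET in the synopsis), and neither matches all the endpoints it governs

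*Protocol*

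**What the plan says.** The protocol describes the analysis twice. For every primary and secondary endpoint, Section 8.1 lists three methods (the paired t-test, the mixed model and GEE), and its sentence on them ends "generalised estimating equations and compared between patients with and without AI therapy". The Statistical Methods row of the Study Synopsis lists the same methods and the same adjustments, but the groups are "compared between patients with and without endocrine therapy".

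The endpoints and groups are set elsewhere:

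- Section 4.3, first primary endpoint: "Changes in visceral adiposity tissue at 12 months in women using aromatase inhibitors versus controls", where controls are women with DCIS or early breast cancer who do not require ET. The synopsis also gives AI versus controls.
- Section 4.3, opening sentence: AI, tamoxifen and control are three groups to be compared.
- Section 4.3 and the synopsis, first secondary endpoint: body composition on tamoxifen versus controls.
- Sections 5.1 and 5.3: 50 AI, 50 controls, and a separate group of 30 on tamoxifen for secondary endpoints.
- Synopsis, remaining secondary endpoints: women on ET versus controls.

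**The concern.** Each methods sentence applies a single two-way split to every endpoint, although the study has three groups. Neither says where the tamoxifen women go, and taken at their word the two sentences put them on opposite sides. Two analysts following the two texts would in general estimate different quantities under the same primary-endpoint label, and the choice could be made after the results are known.

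The protocol itself explains why this matters. Section 3.2.2 faults earlier randomised trials because "Control groups were exposed to ongoing tamoxifen which is an important confounder of changes to body composition and lipid profile". A non-AI comparison group that contains tamoxifen users would repeat that weakness on the same outcomes. The synopsis split has the opposite problem: it mixes tamoxifen into the treated group, whereas the hypothesis in Section 4.2 concerns AI-related oestradiol depletion.

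**Working it through.** **Inputs.** Group sizes 50 AI, 50 control, 30 tamoxifen (Sections 5.1, 5.3). SD 40 cm², two-sided 0.05, power 80%, 40 per group, 30% drop-out, target difference 25% (Section 5.2). The protocol gives no mean, so 25% has no stated value in cm². I take it as 25 cm², which implies a mean near 100 cm².

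**Reproducing the plan's figure.** n per group = 2 × (1.960 + 0.842)² × 40² / 25² = 40.2, rounded up to 41 (41.2 with the t distribution). The stated 40 is reproduced within rounding, so the study was sized for a two-group AI-versus-control comparison, and 25 cm² is consistent with that sizing.

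**What each sentence estimates if read literally.** Let d be the AI effect and t the tamoxifen effect, each versus control. Tamoxifen's share of the pooled side is 30/(50 + 30) = 0.375 in both cases.

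- Section 8.1 (50 AI v 80 others): d − 0.375t. This equals d only if t = 0.
- Synopsis (80 ET v 50 controls): 0.625d + 0.375t. This equals d only if t = d.
- The two agree only if d − 0.375t = 0.625d + 0.375t, that is, t = 0.5d.

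**Which endpoints each split can deliver.** Tamoxifen and control women are both without AI, so the Section 8.1 split cannot produce the tamoxifen-versus-control secondary endpoint on any reading. The synopsis split does not separate AI from tamoxifen, so it does not produce the AI-versus-control primary endpoint.

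**Size.** With d = 25 cm², SD 40 cm² and the 30% attrition named in Section 5.2, completers are 0.7 × 50 = 35 and 0.7 × 80 = 56. Power is for a two-sample t-test.

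| Tamoxifen effect t | Section 8.1 estimates (power, 35 v 56) | Synopsis estimates (power, 35 v 56) |
|---|---|---|
| 0 | 25.0 cm² (0.82) | 15.6 cm² (0.43) |
| 0.5d | 20.3 cm² (0.64) | 20.3 cm² (0.64) |
| d | 15.6 cm² (0.43) | 25.0 cm² (0.82) |

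The comparator is AI versus control at 35 v 35, with power 0.73. The 0.82 exceeds it only because the pooled side is larger, and holds only where pooling happens to introduce no bias. If t lay outside this range the two readings would diverge further: at t = −0.5d, Section 8.1 gives 25 + 0.375 × 12.5 = 29.7 cm² and the synopsis 0.625 × 25 − 0.375 × 12.5 = 10.9 cm².

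**Sensitivity to the assumed mean.** With a mean of 80 cm² (d = 20), power at 35 v 56 runs from 0.30 to 0.63, against 0.54 at 35 v 35. With a mean of 120 cm² (d = 30) it runs from 0.58 to 0.93, against 0.87. The proportional dilution does not depend on the mean: at worst the estimate is 0.625d.

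**The case against.** The strongest reply is that the protocol, read as a whole, largely settles where tamoxifen belongs. Section 4.3 defines controls as women not requiring ET and names three groups, Sections 5.1 and 5.3 reserve tamoxifen for secondary endpoints, and the synopsis lists tamoxifen as a subgroup. On that reading Section 8.1 is loose shorthand for AI versus control. This stands in part: pooling is not certain, and the figures above describe the literal reading only. It does not rescue either sentence for all the endpoints it claims to govern, because the Section 8.1 split still misses tamoxifen versus control and the synopsis split still misses AI versus control.

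A reader might infer that the plan does not test the primary contrast at all, since it begins with "analyzed using paired-sample t-tests, generalised linear mixed models" and a paired test looks only at change within a group. The document does not support that. Mixed models and GEE both compare groups, and the sentence says changes are compared between patients. Nor does any passage say that a significant paired test in one group and not in the other would be taken as a treatment effect.

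Pooling both drugs for the secondary endpoints can also be defended. The study question and the aims in Section 4.1 concern ET as a class, so a pooled analysis is legitimate there. A reader might infer that Section 3.2.5 establishes that tamoxifen's hepatic effects differ from those of AIs. It says only that AI effects are less well described and that one cohort suggests a higher fatty-liver risk with tamoxifen. That is a reason to show the drugs separately as well, not proof that pooling is wrong.

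Finally, much model detail may properly sit in an analysis plan that is not shown. That does not touch a contradiction within the protocol itself.

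**Conclusion.** The point holds as a contradiction between Section 8.1 and the synopsis, and between each of them and the endpoints they cover. Read literally, 37.5% of the pooled side is misplaced relative to the primary contrast, and the estimate falls between 0.625d and d for a tamoxifen effect between nil and the AI effect. In the plan's terms that is 15.6 to 25 cm², with power 0.43 to 0.82 at 35 v 56 against 0.73 for the intended comparison.

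Those figures rest on reading 25% as 25 cm², SD 40 cm², 30% loss in every group, and an unknown tamoxifen effect. The low end is a worst case, not a prediction. The contradiction itself rests on no assumption. Because it concerns the definition of the primary comparison, it should be resolved before any analysis.

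**What to change.** Put one identical sentence in Section 8.1 and the synopsis, stating that:

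- the already listed mixed model uses a three-level group factor (AI, tamoxifen, control), with the adjustments already named;
- the primary contrast is AI minus control at 12 months;
- tamoxifen minus control at 12 months is a separate secondary contrast;
- tamoxifen women are never counted in the AI or the control group for these contrasts;
- paired t-tests are within-group description only.

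A pooled ET-versus-control analysis may stay for the secondary endpoints worded that way, shown beside the separate AI and tamoxifen contrasts.

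The cost is a wording amendment. It needs no new data, visits or participants. The one consequence to accept is that a pooled ET result no longer stands alone for any endpoint.

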9. STORAGE OF BLOOD AND TISSUE SAMPLES

9.1 DETAILS OF WHERE SAMPLES WILL BE STORED, AND THE TYPE OF CONSENT FOR FUTURE USE OF SAMPLES

All laboratory studies aside from sex steroid analyses (using LC-MS) will be performed at Austin Pathology on the same day that blood is collected from participants. The results of these tests will go into the participant's Austin Health medical record and be collected separately in their study file. Blood will be discarded within 14 days of analysis.

Blood for sex steroid analysis will be collected on the same day but will be spun, aliquot and stored in a locked freezer in the Austin Health Endocrine Department laboratory at -80 degrees Celsius. Blood samples will be stored by study number only and external researchers/organisations will not be able to identify participants by this number. At study completion, an aliquot from each participant, from each time point, will be sent as a batch

to the ANZAC Research Institute for sex hormone analysis. Blood samples will be discarded by the ANZAC Research Institute within 14 days of analysis.

If participants give their consent for their blood to be stored for future ethically approved research +/- genetic testing (unspecified consent), the other frozen aliquots will be maintained in a locked Endocrine Department Laboratory freezer indefinitely, for future ethically approved research into disease related to Women's Health. These samples will only be labelled with study number. This freezer is locked and managed by a research scientist. Access to these blood samples is only by certified laboratory technicians employed by the Endocrine Department. Consent for this storage and future ethically approved research +/- genetic testing will be explicitly sought as detailed in the Participant Information Consent Form. For participants who do not provide unspecified consent for future ethically approved research +/- genetic testing, blood will only be stored for sex steroid analysis to be done at study completion.

All collected blood samples will be in an individually re-identifiable form. The code to match study number with identifying participant hospital record number and demographic details will be stored in an electronic file in a password protected area of a University of Melbourne Department of Medicine (Austin Health) server and only study doctors will have access to this file. Access to the University of Melbourne Department of Medicine server requires individual log in details and is controlled and monitored.

10. DATA SECURITY & HANDLING

10.1 DETAILS OF WHERE RECORDS WILL BE KEPT & HOW LONG WILL THEY BE STORED

Paper copy information will be stored in a locked filing cabinet within a locked office located in the University of Melbourne Department of Medicine, Austin Health. Each participant will have a file, which will be identified by study number only.

An electronic database file will also be kept for each participant as backup and as a way to analyse this information. This will also be identified by study number only and stored on a password-protected file on a University of Melbourne Department Medicine Server.

Electronic and paper study files will be stored for 15 years after the end of the study. After that time, electronic information will be permanently deleted. Paper records will be destroyed in Austin Health Confidential Waste bins.

